## **1.5 Research Risks & Benefits**

### **1.5.1 Risk of Avelumab administration**

Most of the observed adverse events (AEs) for Avelumab were either in line with those expected in subjects with progressive advanced solid tumors or with class effects of mAb blocking the PD-1/PD-L1 axis. Infusion-related reactions including drug hypersensitivity reactions and immune-mediated adverse reactions have been identified as important risks for Avelumab. For details regarding the risks and clinical safety profile of Avelumab, see **Section 1.2.8** and the **Dose Rationale, Section 1.4**.

To minimize risk to the subject, vital signs, symptom-directed physical exams and safety labs will be performed at frequent intervals throughout the study and as indicated in the **Schedule of Events (Attachment 1)**. Pre-medication will be given prior to every Avelumab infusion, and risk mitigation measures for infusion-related reactions will be implemented in this study consistent with all ongoing clinical studies with Avelumab. In addition, subjects will be asked to report any potential adverse events and concomitant medications continually throughout the study as indicated in the Schedule of Events, and complete physical exams performed prior to the initiation of every cycle. Furthermore, investigators will be educated on expected **immune-related adverse events (irAE)** as defined in **Section 5.2.3.3** as well as **adverse events of special interest (AESIs)** as defined in **Section 3.4**. A table is included that describes specific irAEs and provides supportive care, dose modification and discontinuation guidelines for Avelumab-related adverse events (**Attachment 4**).

### **1.5.2 Risk with Radiation Therapy (RT)**

Salvage re-irradiation has long been offered as a treatment modality for recurrent GBM patients and has been established to be generally safe and well tolerated (see Section 1.1.4). However, the risk of radiation necrosis and other adverse events listed below are increased in the setting of re-irradiation for glioma.

Expected acute radiation therapy adverse events include skin reaction, including dryness, redness, itching (pruritis), tanning, soreness and hair loss, fatigue, nausea, vomiting, dry mouth, altered taste, decrease in blood counts, short-term hearing impairment due to reactions in the ear canals and on the ear, serous otitis media (fluid in the middle ear) as well as temporary aggravation of brain tumor symptoms such as headaches, seizures, and weakness.

Expected early delayed radiation therapy adverse events (occurring 1-3 months after radiotherapy treatment) include fatigue, lethargy and transient worsening of existing neurological deficits.

CONFIDENTIAL

Expected late delayed radiation therapy adverse events (occurring 3 months or more after radiation therapy treatment) include radiation necrosis (severe local damage to normal brain tissue), which may result in permanent neurocognitive deficits (difficulties with short term memory, calculations, language and more severe neurocognitive deficits) or motor dysfunction, leukoencephalopathy, permanent hearing impairment, radiation injury to the visual structures including the optic nerve and chiasm, which can result in partial or complete blindness, cataracts endocrine dysfunction and radiation-induced neoplasms. Radiation necrosis can mimic recurrent brain tumor and may require surgery for diagnosis and treatment.

To minimize risk to the subject, modern RT techniques will be used including fractionated stereotactic radiotherapy, protons, and IMRT, which allow for highly conformal treatment to a considerably more precise target volume. These technologies have the potential to significantly reduce the toxicity associated with re-irradiation. Fractionated and hypofractionated RT (HFRT) have well-established safety and adverse event profiles and is generally well tolerated in recurrent GBM patients, with uncommon occurrences of late CNS toxicity and radiation necrosis (see **Section 1.1.4**).

### 1.5.3 Potential Overlapping Toxicities with Avelumab and Re-Irradiation

There is a theoretical risk that immunotherapy may potentiate the effects of central nervous system radiation necrosis given that radiation-related central nervous system necrosis is partially immune-mediated. Thus, there is potential for increased frequency of cerebral radiation necrosis and severe neurotoxicity from cerebral radiation necrosis. This potential for overlapping toxicity may also result in an increased risk of surgery for diagnosis and treatment of radiation necrosis.

However, a recent phase I study has demonstrated that HFRT can be safely combined with anti-PD-1 antibody therapy in recurrent high-grade glioma patients and a retrospective study has reported that anti-PD-1 antibody therapy can be safely combined with various hypofractionated radiation prescriptions in melanoma brain metastasis patients.

Therefore, we will conduct a **Safety Lead-in** (see **Section 1.1.5** for rationale) that will include the first 6 subjects to further define the safety and determine the RP2D of Avelumab when combined with HFRT. The dose of Avelumab administered during the safety lead-in will initiate with the established RP2D of Avelumab when administered as monotherapy and incorporates a de-escalation of Avelumab dosing following 3+3 phase I guidelines if unexpected DLT is observed in the first 6 subjects.

### 1.5.4 Other Risks of Study Participation

Beyond the risk of study therapy exposure, subjects will not be exposed to additional risk beyond the risks associated with standard of care safety procedures for recurrent GBM therapy. The study procedures including subject visits, vital signs, phlebotomy approximately every 2 weeks, and imaging/response assessments approximately every 2 months, are equivalent to the procedures that would be performed for standard therapy for recurrent GBM. An alternative course of management would be no interventional therapy and palliative care only. Compared to palliative care, the risks associated with study participation outside of study therapy exposure include the risk of phlebotomy, imaging response assessments including cranial MRI and CT, and visits with practitioners. Risks associated with phlebotomy include weakness, redness, pain, bruising, bleeding, or infection at the needle site. To minimize risk, patients will be counseled on study procedures and associated risks throughout the duration of the study.

CONFIDENTIAL

Risk of harm from genetic testing may be a possibility should the principal investigator identify important findings in the future research and the subject opt into receiving these results. Genetic testing can generate information about a subjects' personal health risks and can cause or increase anxiety, damage family relationships, and/or compromise insurability, employability and can even lead to discrimination. Results will only be disclosed by a qualified genetic counselor under the circumstance that the PI believes they are important for the subject's health, and results will not be shared with employers, insurers, or placed in the subject's medical record, thereby greatly reducing the possibility of psychological or social risks that could arise from knowledge of this genetic information, such as risk for employability or insurability or the risk of discrimination.

### 1.5.5 Potential benefits

The potential benefits to subjects with study participation are improved tumor control and improved overall survival with study participation. Currently there is no effective therapy for secondary, recurrent *IDH* mutant glioblastoma that has transformed after chemotherapy including temozolomide and PCV. No therapy has been proven to improve survival in this setting in a randomized, prospective trial.

## 2 Study Objectives

This is a single arm, open-label phase II study with a 6 patient safety lead-in cohort with the primary objective of determining the safety and toxicities of, and recommended phase 2 dose (RP2D) of Avelumab when administered with HFRT in adults with *IDH* mutant gliomas that have transformed to GBM after temozolomide or PCV chemotherapy. An additional primary objective will be to estimate the PFS6 of the study therapy (Avelumab + HFSRT) in a two stage phase II trial design. Secondary objectives will be to estimate additional measures of efficacy, including 12-month OS, median PFS, radiographic response rate, and median duration of response, as well as explore the association of biomarkers with PFS6, including hypermutation phenotype, proportion of predicted mutation-associated neoantigens, tumor PD-L1 expression, and circulating baseline and changes in Treg and MDSC levels.

[figure not shown]
## 3 Study Design

### 3.1 General Design

[figure not shown]
#### 3.1.1 Study Schema

CONFIDENTIAL

This material is the property of the NYU School of Medicine and Langone Medical Center. Do not disclose or use except as authorized in writing by the study sponsor

### Timeline of Selected Important Events

### 3.1.2 General Study Design

This is a multicenter, single arm, open label, phase II trial of Avelumab and radiation in adult patients with transformed *IDH* mutant GBM with the primary objective of estimating PFS6.

The study will start with a **Safety Lead-In (Section 5.2.1)**, which will be conducted to further define the safety and determine the recommended phase II dose (RP2D) of Avelumab in a subsequent expansion cohort when combined with HFRT. The Safety Lead-In also incorporates a de-escalation of Avelumab dosing if unexpected dose-limiting toxicity is observed in the first 6 subjects and follows a 3+3 phase I design. The first 6 subjects will be considered as a Safety Lead-In and will be observed for dose-limiting toxicities (DLTs) for an evaluation period of 28

CONFIDENTIAL

This material is the property of the NYU School of Medicine and Langone Medical Center. Do not disclose or use except as authorized in writing by the study sponsor

days. The dose of Avelumab administered during the Safety Lead-In will not exceed the established RP2D of Avelumab when administered as monotherapy.

The **Phase II trial (Section 5.2.2)** is a two-stage design study at the Avelumab dose determined to be safe in combination with HFRT (RP2D) in the Safety Lead-in. The phase II trial will enroll a total of 18 subjects in stage 1. In interim evaluation for efficacy will be conducted at the end of stage 1. If the efficacy measures are met, 25 additional subjects will be enrolled in stage 2 for a total planned enrollment in the phase II trial of 43 patients. Monitoring of toxicity will be carefully assessed during the phase II trial (see Primary Safety Endpoints, **Section 3.4**). For study purposes, the occurrence of toxicity attributable to Avelumab that requires discontinuation of Avelumab therapy as defined in **Section 5.2.3.2** is defined as unacceptable. Dose limiting toxicity rates of 40% or less are considered acceptable. Interim analyses of safety will be conducted at 10 patients and again at 18 patients as described in the Primary Safety Endpoints (**Section 3.4**).

After screening procedures and registration, subjects will be treated with one dose of Avelumab (10 mg/kg IV) followed by hypofractionated radiotherapy (HFRT, 5 fractions of 5 Gy each fraction on consecutive days) that initiates 7 days after the first dose of Avelumab. Avelumab will continue to be given once every 2 weeks after the first dose. One treatment cycle is defined as 28 days, corresponding to 2 doses of Avelumab. Subjects will be evaluated every 8 weeks with radiographic imaging to assess response to treatment. The Immunotherapy Response Assessment for Neuro-Oncology (iRANO) criteria (**Attachment 3**), which is based on the immune-related response criteria and the RANO criteria for brain tumor response assessment, will be used as the primary efficacy endpoint of PFS. Adverse events will be monitored throughout the trial and graded in severity according to the guidelines outlined in the NCI Common Terminology Criteria for Adverse Events (CTCAE) version 4.03.

Avelumab administration will continue for 2 years or until progression of disease, unacceptable adverse event(s), intercurrent illness that prevents further administration of treatment, investigator's decision to withdraw the subject, subject withdrawal of consent, pregnancy of the subject, noncompliance with trial treatment or procedure requirements. Expected duration of subject participation is 4 months, which is the median progression-free survival for standard therapy in recurrent GBM.

End of treatment assessments will be performed within 7 days after last drug administration or within 7 days after decision to end treatment. After the end of treatment, each subject will be followed for 30 days for adverse event monitoring and 90 days for serious adverse event reporting. All subjects will be followed until resolution or stabilization of any serious or reportable adverse events occurring during treatment or starting within 30 days of last study drug. Assessments may continue for ongoing reportable adverse events. All subjects will be followed by telephone contact every 3 months or medical record review for overall survival until death.

Specific procedures to be performed during the study, as well as their prescribed times and associated visit windows, are outlined in the **Schedule of Events (Attachment 1)**.

### **3.2 Primary Study Endpoints**

- 1. Determine the safety and tolerability and RP2D of Avelumab when administered with HFRT in adults with *IDH* mutant gliomas that have transformed to GBM after temozolomide or PCV chemotherapy.**

A Safety Lead-In will be conducted that incorporates a de-escalation of Avelumab dosing if unexpected dose-limiting toxicity (**DLT, Section 5.2.1.2**) is observed in the first 6 subjects and follows a 3+3 phase I design for dose de-escalation, if necessary (see **Section 5.2** for details). The first 6 patients will be considered as safety lead-in and observed for an evaluation period of 28 days. Patients who experience DLT will be discontinued from study therapy and will enter the post-study follow-up phase of the study. To be evaluable for a DLT, an individual subject must

CONFIDENTIAL

have received at least the first administration of Avelumab, complete HFRT per protocol and be monitored for at least 28 days following the first Avelumab administration.

The safety analysis will include all subjects who experience toxicities as defined by CTCAE 4.03 criteria. Safety will be assessed by quantifying the toxicities and grades experienced by subjects who have received Avelumab with HFRT, including serious adverse events (**SAEs, Section 8.1**), immune-related adverse events (**irAEs, Section 5.2.3.3**), and adverse events of special interest (**AESIs, Section 3.4**). The frequency, time to onset, and severity of toxicities, as well as the success of standard medical management and dosing interruptions/delays, will be analyzed to determine if a given toxicity should be considered a DLT for dose de-escalation purposes. Adverse events that meet DLT criteria but occur outside the DLT window will be classified as unacceptable AEs and study treatment will be discontinued.

**2. Estimate the PFS6 of Avelumab + HFRT in adults with *IDH* mutant gliomas that have transformed to GBM after temozolomide or PCV chemotherapy**

Once the RP2D has been determined, the phase II portion of the study will be conducted. The phase II trial is a two-stage design, single arm trial to estimate the 6-month progression-free survival PFS6 with Avelumab in combination with HFRT in adults with *IDH* mutant glioma that has transformed to GBM (Grade IV) after prior treatment with temozolomide or PCV (see **Statistical Methods, Section 7.2** for details). PFS6 is a standard outcome measure for recurrent glioblastoma clinical trials. The iRANO criteria (**Attachment 3**), which is based on the immune-related response criteria and the RANO criteria for brain tumor response assessment, will be used to assess the primary efficacy endpoint of PFS6. All subjects that receive at least 1 dose of Avelumab and/or radiation will be included in the primary analysis.

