Diagnosis and Main Inclusion Criteria	Adults with a previously diagnosed lower grade (WHO grade II or III) IDH1/2 mutant glioma that has transformed to glioblastoma (GBM, WHO grade IV) after treatment with temozolomide, CCNU or PCV chemotherapy. Refer to Section 4 for complete Inclusion and Exclusion Criteria.

CONFIDENTIAL

Study Product, Dose, Route, Regimen	

• Avelumab (MSB0010718C) 10 mg/kg intravenously (IV) every 2 weeks

• Hypofractionated radiation therapy to a total dose of 25 Gy, delivered in 5 Gy per fraction for 5 consecutive daily fractions

Duration of administration	Avelumab therapy will continue for up to 2 years if tolerated and or until disease progression, unacceptable toxicity, or withdrawal of consent, whichever comes first.
Reference therapy	The reference therapies are bevacizumab monotherapy and hypofractionated radiation therapy, each of which is a standard single-modality therapy for recurrent GBM.
Statistical Methodology	Primary Efficacy Analysis: Forty three (43) patients will be enrolled and treated in the phase II portion of this trial. With an optimum 2 stage Simon Phase II design, we can test the null hypothesis that $PFS6 \leq 0.40$ versus the alternative that $PFS6 \geq 0.60$ with $\alpha = 0.05$ (actual $\alpha = 0.047$ ) and power of 80% (actual is 82.7%) with a total of 43 patients. If 7 or fewer subjects achieve PFS6 among 18 patients, the study will conclude at the end of stage 1; if 8 or more subjects achieve PFS6, the trial will continue for up to 43 patients. If 23 or more subjects achieve PFS6 in the total of 43 patients, the therapy will be considered interesting for further study.

CONFIDENTIAL

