**PFS6 reference measures:** Previous meta-analyses have demonstrated that PFS6 is an adequate indicator of antitumor benefit for salvage GBM clinical trials and is the standard benchmark used in GBM chemotherapy trials. Published reference outcomes in recurrent GBM report a PFS6 of 9-15%. Temozolomide, the only chemotherapy that has demonstrated improved survival in any prospective, randomized phase III trial in GBM, produced a PFS6 of 21% when tested in recurrent GBM patients. More recently, a number of recently reported randomized, prospective trials in recurrent GBM used conventional cytotoxic chemotherapies such as lomustine and carboplatin for the control arm and have reported remarkably similar estimated PFS6 rates in the chemotherapy control arms, ranging between 15%-25%. Otherwise, bevacizumab, which was granted accelerated approval by the US FDA for use as monotherapy in progressive GBM in 2009 based on two historically-controlled, single-arm or non-comparative phase II trials, has been reported to have relatively higher estimated PFS6 rates of 29% and 42.6%. However, despite improved PFS6 rates observed in phase II trials, the addition of bevacizumab to lomustine failed to show a benefit in overall or neurologic progression-free survival compared to lomustine alone in a multi-institutional, randomized phase III trial of recurrent GBM. Therefore, based on the aggregate results of the above studies, the reference benchmark for our study will be PFS6 of 40%.

**Overall Survival (OS) reference measures:** In recent randomized, controlled trials of recurrent GBM, all of which have failed to demonstrate differences between arms, the median OS of experimental and control arms from the time of recurrence across all of these studies have been remarkably similar and have ranged between 6-10 months, with most arms in these studies reporting a median OS of approximately 9 months. These data indicate the chemotherapies in these studies have similar minimal efficacy in recurrent GBM.

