### **Anti-Tumor Effect Definitions**

Evaluable for objective response. Only those participants who have measurable disease present at baseline (obtained within 14 days of cycle 1, day 1) scan and have received at least one dose of therapy will be considered evaluable for response. These participants will have their response classified according to the definitions stated below. (Note: Participants who exhibit objective disease progression or die prior to the end of cycle 1 will also be considered evaluable.)

Measurable disease. Bi-dimensionally, contrast-enhancing, measurable lesions with clearly defined margins by CT or MRI scan, with a minimal diameter of 1 cm, and visible on 2 axial slices which are at least 5 mm apart with 0 mm skip. Measurement of tumor around a cyst or surgical cavity, if necessary, requires a minimum thickness of 3 mm. If there are too many measurable lesions to measure at each evaluation, the investigator must choose the largest two to be followed before a participant is entered on study. The remaining lesions will be considered non-measurable for the purpose of objective response determination. Unless progression is observed, objective response can only be determined when all measurable and non-measurable lesions are assessed.

Non-measurable evaluable disease. Unidimensionally measurable lesions, masses with margins not clearly defined, lesions with maximal diameter < 1cm.

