#### CONFIDENTIAL

1. Greater than or equal to 50% decrease compared to baseline in the sum of products of perpendicular diameters of all measurable enhancing lesions sustained for at least 4 weeks. In the absence of a confirming scan 4 weeks later, this scan will be considered only stable disease.
2. No progression of non-measurable disease.
3. No new lesions.\*
4. All measurable and non-measurable lesions must be assessed using the same techniques as baseline.
5. Participants must be on no steroids or must not be on increased doses of steroids within 2 weeks of assessment relative to the dose taken at the time of the previous assessment
6. Stable or improved non-enhancing (T2/FLAIR) lesions on same or lower dose of corticosteroids compared to baseline scan.
7. Stable or improved, for clinical signs and symptoms present at baseline and recorded to be disease related clinically.

*Participants with non-measurable disease cannot have a partial response. The best response possible is stable disease.*

*\*See immunotherapy considerations below regarding new lesions*

Progressive disease (PD). Any of the following criterion must be met:

1. 25% increase in sum of the products of perpendicular diameters of enhancing lesions (over best response or baseline if no decrease) on stable or increasing doses of corticosteroids
2. Patients who decrease corticosteroid use within 2 weeks of MRI assessment relative to the dose taken at the time of the previous assessment cannot be classified as having progressive disease and should be classified as non-evaluable.
3. Any new enhancing measurable lesion\*
4. Clear clinical deterioration not attributable to other causes apart from the tumor (e.g. seizures, medication side effects, complications of therapy, cerebrovascular events, infection, etc.). The definition of clinical deterioration is left to the discretion of the investigator but it is recommended that a decline in the Karnofsky Performance Score (KPS) from 100 or 90 to 70 or less, a decline in KPS of at least 20 from 80 or less, or a decline in KPS from any baseline to 50 or less, for at least 7 days, be considered neurologic deterioration, unless attributable to co-morbid events or changes in corticosteroid dose.
5. Failure to return for evaluation due to death or deteriorating condition

*\*See immunotherapy considerations below regarding new lesions*

Stable disease (SD). All of the following criteria must be met:

1. Does not qualify for CR, PR, or progression.

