#### Special Considerations for Immunotherapies.

Appearance of new lesions is a criterion that defines progression of disease by RANO criteria. However, transient appearance of new enhancing lesions at either local or distant sites might occur in patients with neuro-oncological malignancies receiving immunotherapy. In such situations, careful radiological and clinical assessments are warranted. In some cases, new enhancing lesions might represent immune responses directed against infiltrative brain tumor cells. In addition, Immune-related response criteria guidelines for non-brain tumor cancers state that early increases in lesion size or new lesions do not

CONFIDENTIAL

define progressive disease unless further progressive changes are confirmed upon follow-up imaging, provided that patients do not have a clinical decline. Therefore, confirmation to define progressive disease is an important, novel aspect of immune-related response criteria. Additionally, the converse argument, the need of follow-up imaging to confirm a radiographic response, has been an accepted component of most response assessment metrics including RANO.

Confirmation of radiographic progression to define progressive disease in iRANO:

- iRANO recommends confirmation of disease progression on follow-up imaging **3 months after initial radiographic progression** if there is no new or substantially worsened neurological deficits that are not due to comorbid events or concurrent medication, and it is 6 months or less from starting immunotherapy.
- Imaging within the 3-month follow-up can be done as medically appropriate at the discretion of the treating clinician.
- The appearance of new lesions 6 months or less from the initiation of immunotherapy alone does not define progressive disease.
- If follow-up imaging confirms disease progression, the date of actual progression should be back-dated to the date of initial radiographic progression.

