### Treatment Planning/Target Volumes

A GTV will be defined using the CT and MRI images.

The GTV includes the post-operative resection cavity if no residual enhancing or non-enhancing tumor is noted. The GTV also includes any non-enhancing tumor as identified on T2/FLAIR. T2/FLAIR signal consistent with edema is not included in the GTV. Therefore a distinction is made between T2 edema (typically without mass effect, sparing the cortical ribbon, obeying the grey/white junction, etc.) with T2 tumor (mass effect with sulcal effacement, involvement of the grey/white junction, obliteration of the cortical ribbon). Care is made to not include any enhancement or T2 signal on the post-operative scan that is due to post-surgical infarct. Fusion of the pre-operative MRI to determine initial extent of the tumor is helpful.

A PTV expansion that is justified based on image guidance and immobilization will be applied. Regardless of immobilization and localization methods, the PTV expansion should be no larger than 3 mm. Therefore, for stereotactic treatment, the PTV is typically 1 mm. For non-stereotactic treatment with IGRT, then the PTV is typically 3 mm.

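### Patients without measurable disease at baseline count in PFS6, but the numbered progression list in Attachment 3 has no item for growth of non-measurable disease, so some such growth is scored as stable

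*Combined protocol and SAP*

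**What the plan says.** **Who can enter.** Sections 4.1 and 4.2 set an upper limit on tumour diameter (4 cm) but no lower one, and nowhere require measurable or residual disease. Resection is allowed up to two weeks before study drug. Attachment 6 plans for a patient with nothing visible left: "The GTV includes the post-operative resection cavity if no residual enhancing or non-enhancing tumor is noted".

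**Who is counted.** Section 3.2, on PFS6: "All subjects that receive at least 1 dose of Avelumab and/or radiation will be included in the primary analysis". Section 7.3.2 likewise sets no measurable-disease condition. Measurability matters only for objective response, where Attachment 3 and Section 6.9 begin the evaluable set with "Only those participants who have measurable disease present at baseline". Section 7.2.2 plans no PFS6 analysis by baseline measurability.

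**How progression is defined.** The numbered list in Attachment 3 has two imaging routes. The first is "25% increase in sum of the products of perpendicular diameters of enhancing lesions (over best response or baseline if no decrease"). The second is a new, measurable, enhancing lesion. The remaining routes are clinical deterioration, and failure to return because of death or decline. The immunotherapy section of Attachment 3 qualifies the second route: "The appearance of new lesions 6 months or less from the initiation of immunotherapy alone does not define progressive disease". It recommends confirming early radiographic progression on imaging three months later, and back-dates confirmed progression to its first appearance. The closing summary table of response criteria also lists new lesions and marked T2/FLAIR worsening as progression.

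**What else is a failure.** Under Section 7.1.3, a patient who does not stay on treatment through six cycles is a failure in the primary analysis.

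**The concern.** Attachment 3 defines a class of non-measurable but evaluable disease: lesions measurable in one dimension, masses with unclear margins, and lesions under 1 cm. The second condition for partial response requires that such disease has not progressed, but the progression list never says what that progression is. Stable disease is defined as whatever does not qualify for response or progression, provided the patient is clinically stable and all sites were assessed. Growth with no matching progression item therefore becomes stable disease.

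PFS6 is the primary efficacy endpoint, and a single-arm count of successes is compared with a fixed 40%. A patient whose tumour grew but whose growth could not be classified adds a success to that count. No control arm shares the same scoring rule, and no planned analysis would show how much of a positive result came from such patients.

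**Working it through.** **Step 1: follow each baseline state through the numbered list.**

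| Baseline enhancing disease | 25% bidimensional increase | New measurable enhancing lesion | Result |
|---|---|---|---|
| Measurable | Works | Works, with confirmation and back-dating | Progression can be scored |
| None (clean cavity) | Undefined: change from zero | Works, with confirmation and back-dating | A route exists |
| Under 1 cm, two diameters obtainable | Arguably works: the item says enhancing, not measurable, lesions | Growth of a known lesion is not clearly new | Ambiguous |
| One-dimensional or ill-defined | Unusable: no reliable product of diameters | Growth of a known lesion is not clearly new | No item; stable by default |

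The last row is the definite gap. T2/FLAIR worsening could fill part of it, but appears only in the summary table and not in the numbered list, so two parts of the same attachment give different rules.

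**Step 2: reproduce the design.** Inputs from the Study Summary and Section 7.1.3: null 0.40, alternative 0.60, stop at 7 or fewer of 18, success at 23 or more of 43. The probability of declaring success at a true rate p is

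P(p) = sum over x = 8 to 18 of Bin(x; 18, p) × Pr[Bin(25, p) ≥ 23 − x].

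- P(0.40) = 0.0474, against a stated 0.047.
- P(0.60) = 0.8272, against a stated 82.7%.

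Both agree. The probability of stopping at stage 1 under 0.40 is 0.563.

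**Step 3: sensitivity to under-called progression.** Suppose true PFS6 is 0.40 for everyone, but a share f of patients is scored a success with probability q. Then the effective rate is p = 0.40(1 − f) + qf.

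| f | q | p | P(declare success) | P(stop at stage 1) |
|---|---|---|---|---|
| any | 0.4 | 0.40 | 0.047 | 0.563 |
| 10% | 0.5 | 0.36 + 0.05 = 0.41 | 0.062 | 0.529 |
| 10% | 0.6 | 0.36 + 0.06 = 0.42 | 0.080 | 0.494 |
| 10% | 0.8 | 0.36 + 0.08 = 0.44 | 0.128 | 0.425 |
| 20% | 0.5 | 0.32 + 0.10 = 0.42 | 0.080 | 0.494 |
| 20% | 0.6 | 0.32 + 0.12 = 0.44 | 0.128 | 0.425 |
| 20% | 0.8 | 0.32 + 0.16 = 0.48 | 0.270 | 0.297 |

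Of 43 patients, 10% is about 4 and 20% about 9. The documents give neither f nor q.

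**The case against.** A reader might infer that no imaging criterion works for these patients. The documents do not support that. Enhancing regrowth in a clean cavity fits the new-lesion item, and the six-month restriction does not cancel that item. It calls for confirmation, after which the event is dated to its first appearance, so a confirmed early recurrence is a PFS6 failure. The three-month confirmation is also not peculiar to this group: early growth of a measurable lesion, without neurological worsening, waits for it too. The summary table offers further routes. All of this stands, and it narrows the gap to growth of disease that was present but non-measurable at baseline, plus the mismatch between list and table.

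A reader might also infer that most of these patients will be scored as successes. That does not follow either. Death, clinical decline and leaving treatment before six cycles are all failures, and these limit the bias. Nothing in the documents fixes q, and at q = 0.4 there is no inflation.

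Finally, the calculation cannot separate under-called progression from a genuinely better outcome after resection. Section 7.1.1 says "the reference benchmark for our study will be PFS6 of 40" percent, but does not say whether the studies behind it included resected or non-measurable patients. A mismatch with the benchmark on this ground is therefore unproven.

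These points do not remove the default to stable disease, which follows from the wording of the list.

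**Conclusion.** The point holds as a defect in the endpoint definition. Patients with non-measurable baseline disease are admitted and counted, the numbered list has no item for growth of that disease, and the stable category absorbs it. For a patient who completes six cycles without clinical decline, growth of one-dimensional or ill-defined disease can be recorded as a PFS6 success. The list and the summary table also disagree on T2/FLAIR worsening.

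The direction of bias is towards success. Its size cannot be determined from the documents. The false-positive range of 6.2% to 12.8% (f = 10%) or 8.0% to 27.0% (f = 20%), for q between 0.5 and 0.8, shows only how sensitive the decision rule is. It is not an estimate of this trial's error rate and should not be quoted as one. The stated alpha and power are correct for the design as specified.

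**What to change.** Both changes concern endpoint scoring only and leave treatment decisions as they are.

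1. **Attachment 3.** Add to the numbered progression list unequivocal progression of non-measurable enhancing disease, including growth to measurable size, under the existing iRANO confirmation and back-dating. Reconcile the numbered list with the summary table, so that T2/FLAIR worsening has the same status in both.
2. **Section 7.2.2.** Add a sensitivity analysis giving PFS6 with its exact 95% confidence interval in patients with measurable enhancing disease on the baseline MRI, and state in advance that the report will say whether a positive pooled result holds there.

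The cost is wording in two places and one extra table. The baseline MRI is already required, and the sample size and decision boundaries do not change. The downsides are a wider interval in the measurable-disease subset and a pooled PFS6 that may be slightly lower once the missing progressions are counted.
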